All participants will be interviewed in person, upon enrollment, prior to randomization, by a trained study team member. At the enrollment visit, baseline data will be collected on demographics, bio-psychosocial status, as well as COPD knowledge, self-management skills, patient activation, and health literacy levels. Participants will then be interviewed via phone by a research team member, who is blinded to their study group assignment at 3-, 6-, and 9-months post enrollment. Similarly, we will collect data from caregiver participants who will be surveyed upon enrollment, and at 3-, 6-, and 9-months follow up post enrollment. Due to the study end date, it will not be possible to collect 9-month follow-up data for participants who enrolled later in the study.

Additionally, information will be collected post enrollment on whether the patient has visited the ED or been re-hospitalized via Chesapeake Regional Information System for our Patients (CRISP). CRISP will be used determine whether the visit was COPD-related using a set of pre-determined discharge diagnoses.

Study Outcomes and Hypotheses

The study groups will be compared for the following outcomes:

Primary Outcome for Patient Participants:

1. Change in health-related quality of life (HRQOL) as measured by the St. George Respiratory Questionnaire (SGRQ) total score, from baseline to 6 months post-enrollment.

Hypothesis: Patients in the HCP PLUS Peer Support group will have a larger improvement in HRQOL (larger negative change in SGRQ score) at 6 months post discharge compared to baseline, than patients in the *HCP only* group.

Secondary Outcomes and Intermediate Measures for Patient Participants:

Secondary Outcomes:

1. Change in HRQOL based on SGRQ total score at 9 months post enrollment.

Hypothesis: Patients in the HCP PLUS Peer Support group will have larger improvement in HRQOL (larger negative change in SGRQ score) compared to baseline, than patients in the *HCP only* group.

2. Total number of COPD-related hospitalizations and ED visits at 3, 6, and 9 months post-enrollment.

Hypothesis: Patients receiving the HCP PLUS Peer Support will have a lower rate of COPD-related hospitalizations and ED visits than patients in the *HCP only* group.

3. Total combined number of *all cause* hospitalizations and ED visits at 3, 6, and 9 months post-enrollment.

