Hypothesis: Patients receiving the HCP PLUS Peer Support will have a lower rate of hospitalizations and ED visits than patients in the *HCP only* group.

4. Total combined number of *all cause* hospitalizations and ED visits at 3, 6, and 9 months post-enrollment.

Hypothesis: Patients receiving the HCP PLUS Peer Support will have a lower total number of *all cause* hospitalizations and ED visits than patients in the *HCP only* group.

5. Change in HRQOL based on SGRQ domain scores at 3, 6, and 9 months post-enrollment.

Hypothesis: Patients receiving the HCP PLUS Peer Support will have larger improvement in HRQOL (larger negative change in SGRQ score) compared to baseline, than patients in the *HCP only* group.

6. Mortality rate at 3, 6, and 9 months post-enrollment.

Hypothesis: Patients receiving the HCP PLUS Peer Support will have a lower mortality rate compared to patients in the *HCP only* group.

Intermediate Measures:

7. Change in PROMIS support domain scores (Instrumental, Informational, Depression, Anxiety, Social Isolation, and Emotional Support) at 3, 6, and 9 months post-enrollment.

Hypothesis: Patients receiving the HCP PLUS Peer Support will have larger positive change in PROMIS scores compared to baseline, than patients in the *HCP only* group.

8. Change in Herth Hope Index total score at 3, 6, and 9 months post-enrollment.

Hypothesis: Patients receiving the HCP PLUS Peer Support will have larger positive change in Hearth Hope Index scores compared to baseline, than patients in the *HCP only* group.

9. Change in Patient Activation Measure (PAM) scores at 3, 6, and 9 months post-enrollment.

Hypothesis: Patients receiving the HCP PLUS Peer Support will have larger positive change in PAM scores compared to baseline, than patients in the *HCP only* group.

10. Change in patient's understanding and self-efficacy, as measured by the *Understanding COPD questionnaire's* three components (About COPD, Symptom Management, and Accessing Help and Support) at 3, 6, and 9 months post-enrollment.

Hypothesis: Patients receiving the HCP PLUS Peer Support will have larger positive change in understanding and self-efficacy levels compared to baseline, than patients in the *HCP only* group.

11. Morisky adherence levels at 6 months post-enrollment.

Hypothesis: Patients receiving the HCP PLUS Peer Support will have a higher level of adherence compared to patients in the *HCP only* group.

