12. Participation in pulmonary rehabilitation at 3, 6, and 9 months post-enrollment.

Hypothesis: Patients receiving the HCP PLUS Peer Support will have greater level of participation in pulmonary rehabilitation than patients in the *HCP only* group.

13. Change in smoking status at 3, 6, and 9 months post-enrollment.

Hypothesis: Patients receiving the HCP PLUS Peer Support will have a higher smoking cessation rate than patients in the *HCP only* group.

Handling of Missing Data (PCORI [name]-4)

There are two types of missing data, at the respondent level (unit non-response) and at the specific question level (item non-response). At the respondent level, missing data occurred because of patient death, withdrawal from study, or inability to be reached via phone for an interview. Comparisons of missingness by several patient characteristics at baseline will be performed with Fisher's exact or Chi-Square tests to examine any potential systematic pattern to the missing data. For the specific case of the SGRQ instrument, values of 100 (the worst possible QoL score) will be imputed for any assessment in which a patient was not available because of death.

With respect to data at the specific question level, missing data will be handled according to each instrument collection manual. In some cases, for example the SGRQ,¹ PAM,² and PROMIS-anxiety,³ -depression,⁴ -emotional,⁵ and -instrumental support index⁶ score will be prepared in instrument specific calculators, provided by the instrument's authors, and accounted for any assignments of missing scores based on the availability of item responses. Missing data for other instruments such as PROMIS-social isolation⁷ and -informational support index⁸, understanding COPD⁹, and Morisky measure,¹⁰ will be handled according to the instrument's author's direction.

When no information is available for handling missing item responses on a particular instrument, a rule, allowing no more than 25% of the items for the scale/domain to be missing, was used. If less than 25% of the item responses were missing, the mean of the non-missing item responses

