was calculated and was used to replace the value of the missing item responses before calculation of the scale/domain score. This approach weights the scale/domain score towards the respondent's mean response and is balanced by requiring a large majority of item responses to be available. If more than 25% of the item responses were missing, the scale/domain score was considered missing.

Statistical Analysis (PCORI Standard IR-1, RC-4)

Statistical summaries and distributions of patient characteristics will be reviewed by study site (JHBMC and HCGH) and by recruitment setting (inpatient and outpatient). Statistical summaries and distributions of patient and clinical characteristics will also be reviewed across study groups. Randomization of the patients to the study groups expects that on average the groups were balanced on characteristics that might affect the study results, such as socio-demographic and health status. Thus, no statistical tests to compare the groups on patient characteristics will be performed.¹¹

Exploratory analyses will be performed cross-sectionally at baseline, 3, 6, and 9 months post-discharge for each of the outcomes across the two study groups. This will provide an assessment of the outcomes' distributions, missingness patterns and the need for additional data review and quality assurance.

The main analysis approach for assessing the change in the primary outcome measure from baseline, as well as changes in secondary outcome measures from baseline, will consist of performing analyses of the treatment effect between the two study groups under intention to treat (ITT) adjusted for baseline measure, site, and recruitment setting.

Repeated outcomes in this study will be evaluated using generalized linear mixed random-effects (RE) models. The generalized linear mixed RE model reflects the study's interest in comparisons of change at the individual level, where the changes may be subject-specific and reflective of potentially unmeasured variables. This model also fits well with the approaches related to

missing data and heterogeneity of treatment effects discussed below. In particular, this approach will help us handle the missing 9-month data for participants who enrolled later in the study.

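### The SGRQ death score of 100 is not limited to visits due before study end, so read literally only late enrollees who die have a 9-month score

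*Combined protocol and SAP*

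**What the plan says.** Three statements in the SAP bear on a late enrollee's 9-month SGRQ.

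- Data Collection for Phase 2: because of the study end date, "it will not be possible to collect 9-month follow-up data for participants who enrolled later in the study".
- Handling of Missing Data: "values of 100 (the worst possible QoL score) will be imputed for any assessment in which a patient was not available because of death". The same paragraph gives the causes of unit non-response: "missing data occurred because of patient death, withdrawal from study, or inability to be reached via phone for an interview". Study end is not among them.
- Statistical Analysis, on the generalized linear mixed random-effects model: "this approach will help us handle the missing 9-month data for participants who enrolled later in the study".

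The outcome concerned is the first secondary outcome, "Change in HRQOL based on SGRQ total score at 9 months post enrollment". The 9-month SGRQ domain scores (item 5 of the same list) follow the same rules. The outcomes table in protocol section 7b takes deaths from caregivers, hospital and ED records and vital statistics, so a death can be known without a 9-month interview.

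**The concern.** Take two patients who enrolled 7 months before the study ended. One dies at month 4 and the other survives. Under the literal death rule the first has a 9-month SGRQ of 100. The second has none, because the study closed before the visit. Among late enrollees, the only 9-month scores are then those of patients who died.

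Late enrolment alone would be a benign reason for missing data, and a mixed model copes well with it. The death rule changes that: it makes the presence of a 9-month value depend on the event that sets the value to 100.

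Nine months is the only scheduled assessment after the 6-month peer programme, so it carries the question of whether any benefit lasts. The SAP also hypothesises lower mortality with peer support. If that proved true, the distortion would add to the apparent SGRQ benefit of that arm. Whether 100 is a suitable score for death is a separate matter; the issue here is its use at a visit that could not have taken place.

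**Working it through.** The plan gives no figure for this effect, so there is none to reproduce. The size has to be shown over assumed values.

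**Inputs from the documents.** 145 patients per arm, 15% attrition, within-patient correlation 0.8, difference of 4 points, power 0.80, alpha 0.05 (protocol section 7c); SGRQ minimum important difference 4 (protocol, Study Measures and Outcomes).

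**Not in the documents, so assumed.** The share of late enrollees L; 9-month mortality m; the SD; a mean of 50 among the living, with no treatment effect on it. The SD can be back-solved from 145 per arm, taking a two-sided test. An SD of 17.7 gives an SD of change of 17.7 × √(2 × 0.2) = 11.19, then n = 123 per arm, and 123/0.85 = 145. The simulation in step 2 uses a between-patient SD of 16 and a within-patient SD of 8, so the correlation is 256/320 = 0.8 and the total SD √320 = 17.9.

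**Step 1: share of deaths among observed 9-month scores, by hand.** Late enrollees are under observation for about 7.5 of the 9 months, so their observed mortality is m' = m × 7.5/9. Under the literal rule:

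observed share dead = [(1 − L)m + L·m'] / [(1 − L) + L·m']

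For m = 6%, m' = 5%:

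- L = 10%: 0.059/0.905 = 6.5%
- L = 30%: 0.057/0.715 = 8.0%
- L = 50%: 0.055/0.525 = 10.5%

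Now compare arms with m = 12% and 6%. A death moves the score from about 50 to 100, so the true contrast is −(0.12 − 0.06) × 50 = −3.0. Using observed scores alone:

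- L = 10%: −(0.1297 − 0.0652) × 50 = −3.22, excess 0.22
- L = 20%: −(0.1415 − 0.0716) × 50 = −3.49, excess 0.49
- L = 40%: −(0.1750 − 0.0903) × 50 = −4.23, excess 1.23

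**Step 2: what the mixed model leaves.** The model uses each patient's other scores and so removes part of this. Large simulations of the 12% against 6% case, fitted by maximum likelihood, gave these 9-month contrasts:

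| Late share | Truth | Literal rule, random intercept | Literal rule, unstructured covariance | All late enrollees missing (random intercept) |
|---|---|---|---|---|
| 20% | about −3.0 | about −3.3 to −3.4 | −3.15 | −2.94 to −2.99 |
| 40% | about −3.0 | −3.8 to −3.9 | −3.35 to −3.37 | −2.90 to −2.99 |

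At 10% late the excess is about 0.1 to 0.2 points. The SAP does not name a covariance structure, so both are shown.

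**Step 3: equal mortality.** With 9% in both arms the true within-arm change is 0.09 × 50 = 4.5. The literal rule with a random intercept gives about 5.0 at 20% late and 6.0 at 40%. The shift is the same in both arms, so the contrast has no bias.

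**Step 4: a wider range.** A second simulation used SD 17.7, with the risk of death rising with baseline SGRQ. Over mortality of 3% to 10%, within-arm bias towards worsening was:

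- 10% late: 0.1 to 0.2 (random intercept), 0.05 to 0.14 (unstructured)
- 30% late: 0.3 to 0.9, 0.2 to 0.5
- 50% late: 0.6 to 2.0, 0.4 to 1.0

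With every late enrollee left missing at 9 months, the bias was within about 0.2 points in all scenarios, which is simulation noise.

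**The case against.** The strongest reply is that the SAP never says a late enrollee who dies is scored 100 at 9 months. That visit was impossible because of study end as well as death. The data-collection sentence makes no exception for deaths, and the analysis section treats late enrollees' 9-month data as missing and leaves them to the model. Read together, these passages can mean that all late enrollees are missing at 9 months, dead or alive, and then there is no bias. This stands as a possible reading. It does not settle the matter, because the death rule covers any assessment and study end is not a listed cause of missing data. A programmer could follow either reading.

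The second reply concerns size. The SAP's hypothesis is between groups, and equal mortality and late share leave that contrast unbiased. At 145 per arm the standard error of the 9-month contrast is about 2.4 (20% late) to 2.8 (40% late), so even the random-intercept excess in the 12% against 6% case is about 0.15 to 0.32 standard errors. It would come from few patients: about 145 × 0.2 × 0.10 = 2.9 late deaths against 145 × 0.2 × 0.05 = 1.5 at 20% late, and about twice that at 40%. This stands, and it is why the point is minor.

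A reader might also infer that the outcome "Mortality rate at 3, 6, and 9 months post-enrollment" is wrong in the same way. The documents do not support that. Nothing says late deaths would be counted against a denominator without late survivors, and the sources for mortality do not depend on the 9-month interview.

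**Conclusion.** The point holds as a defect of wording. On the literal rule, a late enrollee's 9-month SGRQ exists only if the patient died, and the planned mixed model reduces the resulting bias without removing it. Within-arm 9-month worsening is then overstated. The between-arm contrast, for the total score and for the domain scores, is exaggerated in favour of the arm with fewer deaths, and only if mortality or late share differs by arm.

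Under the assumed 12% against 6% mortality, the excess runs from about 0.1-0.2 points at 10% late to 0.2-0.4 at 20% and 0.4-0.9 at 40%. The lower end is for an unstructured covariance and the upper for a random intercept. All of this is small beside the 4-point important difference, and it rests on mortality and late shares that the documents do not give.

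It would go too far to say that the 9-month treatment comparison is wrong whatever happens, or that the primary result is at risk. The first fails with equal mortality and late share, or on the other reading of the rule. The second fails because the SAP confines the gap to 9-month data. Severity: minor, secondary time point.

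**What to change.** Amend the death rule in the SAP's Handling of Missing Data section in three respects.

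- Impute 100 for death only where the scheduled assessment date (enrolment plus 3, 6 or 9 months) falls on or before the study end date.
- Where the 9-month date falls after study end, set the 9-month SGRQ to missing, whether the patient is dead or alive.
- Add study end to the listed reasons for missing data.

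Reporting the number of late enrollees and of deaths among them by arm would let a reader see how much the rule matters.

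The cost is a sentence or two in the SAP and one programming condition on dates already held. A few late deaths no longer contribute a 9-month score.

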The study participants are adults receiving treatment for COPD and their family caregivers. The patient participants must be older than 40 years, with no significant cognitive dysfunction, severe mental illness, or active substance abuse. Family caregivers must be 18 years or older and chosen by the patient participant to get enrolled with them into the study. The reason for these requirements is the nature of the proposed intervention (group-based with active engagement and participation).

[figure not shown]
We will conduct this study at Johns Hopkins Bayview Medical Center (JHBMC) and Howard County General Hospital (HCGH), and their affiliated pulmonary and primary care clinics (some of these clinics are part of Johns Hopkins Community Physicians). JHBMC is an academic center in Baltimore, Maryland that serves an urban, inner-city population with a large percentage of low-income and ethnic minority patients, as well as patients from the Baltimore-

Washington DC region. JHBMC has a 550-bed hospital, a nationally recognized pulmonary center, pulmonary specialty clinics, a pulmonary rehabilitation center, and multiple primary care clinics. HCGH is a community hospital in Columbia, Maryland that serves a suburban population with a large percentage of middle class patients, as well as patients from the Baltimore-Washington DC region. HCGH is a 300 bed community hospital, and includes pulmonary specialty clinics, a large pulmonary rehabilitation center (about 2000 people complete the acute rehabilitation program), and multiple primary care clinics. Both hospitals and their affiliated clinics are part of the Johns Hopkins Health System.

Study structure

We will conduct a randomized controlled trial (RCT) to implement and test study interventions at two study sites, recruiting COPD patient participants from an urban academic hospital (Johns Hopkins Bayview Medical Center) and its affiliated hospital based clinics and a suburban hospital (Howard County General Hospital) and its affiliated clinics. Participants will be recruited from both hospital and ambulatory service settings.

Below is a schematic depicting Phase 2 trial design:

* Randomize within site and service setting

In the HCP Arm, we will employ a healthcare professional delivered, clinic-based approach for engaging patients and families. It involves delivery of self-management education and support on an individual basis to individual patients (and their family caregivers, if applicable).

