together, participated in a BREATHE call, or by having a phone conversation with their BREATHE pal containing discussion of COPD-related issues (determination based on BREATHE pal notes.) For a more detailed description of our complier-average causal effect analysis and IV approach, please refer to the statistical analysis plan in the supplemental study documents section (SAP_BREATHE2_2019Jun26).

The sample size calculation will be based on an overall comparison of the change between the baseline and 6-month measurements of the patients on the St. George scale (primary outcome) in the two arms (interaction term). The unadjusted per-arm sample size is based on a power of 0.80, alpha of 0.05, a minimally clinical significant difference in change scores of 4 points and a meta-analysis estimate of variability. The estimated sample size is 145 patients per arm, after accounting for a 15% attrition rate, assuming a within-patient correlation between measurements of 0.8.

Heterogeneity of Treatment Effects (HTE) HT-1

The goal of the HTE analyses in this study is to consider the difference in treatment effect between the two arms, taking into consideration differences in the arms that are not obviously accounted for in the balance created by the randomization scheme. Patient characteristics such as disease severity or caregivers' presence may show differences in the intervention's effect and thus are important avenues to explore for hypothesis generation. In this hypothesis generating HTE analysis, we will consider the following subgrouping variables: age (4 categories), gender, disease severity, baseline PAM score, and caregiver presence. Within the HCP PLUS Peer Support group, we will also consider subgrouping by the propensity for adherence to treatment.

HT-2, HT-3

Subgroup treatment effects will be estimated by including a three-way interaction between the subgroup variable, the study assignment variable, and the 6-month time variable in a generalized linear mixed RE model. We will test for a difference in treatment effect between subgroups by a hypothesis test of the overall three-way interaction in this model. We will report estimates of subgroup treatment effects with corresponding 95% confidence intervals (CIs). For a more detailed description of the heterogeneity of treatment effect, please refer to the statistical analysis plan in the supplemental study documents section (SAP_BREATHE2_2019Jun26).

- d. Early stopping rules.
No early stopping rules.

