The primary repeated outcome (SGRQ) will be evaluated using a linear mixed RE model. Within this model, the primary hypothesis about change in HRQOL from baseline to 6 months, will be evaluated by a hypothesis test of the interaction term between study group and the 6-month time variable.

For secondary outcomes, we will fit appropriate generalized linear mixed RE models based on the type of outcome variable. Continuous measures, such as for HERTH Hope Index or PROMIS support domain scores, will be assessed using linear mixed RE models. Binary outcomes, such as Morisky adherence to medication, will be assessed using logistic mixed RE models. Outcomes that are cumulative counts, such as number of hospitalizations and ED visits, will be assessed using Poisson or negative binomial mixed RE models, as appropriate. Differences in change in outcome from baseline to 3, 6, and 9-months between the study groups will be assessed by including interaction terms between the time variables and study group. We will assess significance by first testing the overall interaction between time and group. If the overall interaction is significant for an outcome measure, we will then estimate and test individual time differences accounting for multiple testing using a Bonferroni correction. Initially models will be adjusted only for baseline measure, site, and recruitment setting. We will also consider adjusting for patient characteristics such as age, gender, presence of caregiver, home oxygen use, and prior hospitalization.

Unadjusted survival analyses using Kaplan-Meier and log rank tests will be performed for *time to death or first COPD-related hospitalization or ED visit*. Statistical significance will be considered for $p < 0.05$.

Complier-Average Causal Effect (CACE) using Instrumental Variable Estimation

CACE: Primary Outcome

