gender, disease severity (whether they are on continuous home oxygen), baseline PAM score (collapsed into low vs high levels), and caregiver presence (caregiver vs no caregiver). Within the HCP PLUS Peer Support group, we will also consider subgrouping by the propensity for adherence to treatment (collapsed into low vs high levels), with propensity for adherence to treatment as the estimated probability of adherence to treatment from our intervention implementation analysis described above.

HT-2, HT-3:

Subgroup treatment effects will be estimated by including a three-way interaction between the subgroup variable, the study assignment variable, and the 6-month time variable in a generalized linear mixed RE model. We will test for a difference in treatment effect between subgroups by a hypothesis test of the overall three-way interaction in this model. We will report estimates of subgroup treatment effects with corresponding 95% confidence intervals (CIs). For the comparison of propensity for adherence groups within the HCP PLUS Peer Support group, we will include an interaction between the subgroup variable and the 6-month time variable, test this interaction, and estimate subgroup effects with corresponding 95% CIs.

References

1. Jones PW. St George's Respiratory Questionnaire Manual. 2009;44(June):0-16.
3. PROMIS. Anxiety. A brief guide to the PROMIS Anxiety instruments. 2018:1-18.
4. PROMIS. Depression. A brief guide to the PROMIS Depression instruments. 2018:1-18.
5. PROMIS. Emotional Support. A brief guide to the PROMIS Emotional Support instruments. 2017:1-6.
6. PROMIS. Instrumental Support. A brief guide to the PROMIS Instrumental Support instruments. 2017:1-6.
7. PROMIS. Social Isolation. A brief guide to the PROMIS Social Isolation instruments.

2015:1-7.

8. PROMIS. Informational Support. A brief guide to the PROMIS Informational Support v2.0 instruments. 2015:1-7.

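### The primary SGRQ model is not written out: on the conventional reading the promised covariate adjustment drops out of the group-by-6-month estimate, and using baseline as both outcome and covariate makes the standard error too small

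*Combined protocol and SAP*

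**What the plan says.** The SAP (Statistical Analysis) sets the main approach for primary and secondary outcomes as "performing analyses of the treatment effect between the two study groups under intention to treat (ITT) adjusted for baseline measure, site, and recruitment setting". For the primary outcome it then says "The primary repeated outcome (SGRQ) will be evaluated using a linear mixed RE model", and that the hypothesis about change to 6 months "will be evaluated by a hypothesis test of the interaction term between study group and the 6-month time variable". Protocol section 7.c says the same and refers to the SAP for detail. The SAP's secondary-outcome paragraph repeats the covariates: "Initially models will be adjusted only for baseline measure, site, and recruitment setting".

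Three other places bear on how to read this.

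- The sample-size paragraph in protocol section 7.c compares the "change between the baseline and 6-month measurements of the patients on the St. George scale (primary outcome) in the two arms (interaction term"). This supports baseline SGRQ being an outcome row and the reference visit.
- For propensity subgroups within the peer-support arm, the SAP's heterogeneity section says "we will include an interaction between the subgroup variable and the 6-month time variable, test this interaction". Those subgroups are not randomised, so that model needs a main effect. The parallel form suggests, but does not prove, that the primary model keeps one too.
- The design schematic (protocol 4.a, Study structure) notes "Randomize within site and service setting".

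Neither document states the outcome rows, whether baseline is outcome, covariate or both, whether a group main effect is kept, whether covariates interact with visit, or which random effects are used.

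**The concern.** Baseline SGRQ, site and setting are constant within a patient. A group-by-visit term with baseline as reference is a within-patient contrast, so main-effect covariates should not move it. The SAP would then promise an adjustment that its own primary test does not deliver.

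Two analysts following the text could also fit different models and report different primary estimates and p-values. Some of those models would have standard errors that are too small, and one would test a different contrast. The SAP also states "Exploratory analyses will be performed cross-sectionally at baseline, 3, 6, and 9 months post-discharge for each of the outcomes across the two study groups", so outcomes will be seen by group while the model is still open.

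**Working it through.** **Inputs.** From protocol 7.c: 145 per arm, 15% attrition, power 0.80, alpha 0.05 (taken as two-sided), 4 points, within-patient correlation ρ = 0.8. No SD is printed.

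**1. The plan's 145.** 145 × 0.85 = 123.25, so 123 evaluable per arm. From n = 2(1.960 + 0.842)² SDc² / 4², SDc = √(123 × 16 / (2 × 7.849)) = 11.2. With SDc = σ√(2(1 − ρ)), σ = 11.2 / √0.4 = 17.7. The 145 can be recovered only by choosing this SD. Other conventions give 17.9 (inflating by 1.15) or 18.6 (baseline-adjusted formula).

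**2. Cancellation.** Conventional model: Y_ij = μ_j + γG_i + δ_jG_i + βX_i + u_i + e_ij. Then Y_i6 − Y_i0 = (μ_6 − μ_0) + δ_6G_i + (e_i6 − e_i0), and βX_i is gone. In simulated complete data with two, three or four visits, estimates with and without the covariates differ by less than 1e-11. With about 15% missing follow-up, site and setting move the estimate by at most 0.20 points. Adding baseline moves it by 0.08 to 0.14 on average (maximum 0.64).

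**3. Precision forgone.** The variance is 2(1 − ρ)σ² for change and (1 − ρ²)σ² baseline-adjusted, a ratio of 2/(1 + ρ) = 1.11. At 123 per arm the standard errors are 1.427 and 1.354, giving power 0.80 and 0.84. The saving is 10%, or about 29 of 290 patients. At the same SD but other correlations (assumed), power is 0.43 against 0.53 (ρ = 0.5), 0.63 against 0.70 (0.7) and 0.977 against 0.982 (0.9).

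**4. Baseline as both outcome and covariate.** With rows at 0 and 6 months the random-intercept variance is estimated as zero, so the fit is ordinary least squares with one slope b on baseline.

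- b = (145 + 123 × 0.8) / 268 = 0.908.
- Residual variances in units of σ²: (1 − b)² = 0.0084 at baseline; 1 + b² − 2bρ = 0.3717 at 6 months.
- Pooled: (145 × 0.0084 + 123 × 0.3717) / 268 = 0.175.
- Model SE: √(0.175 × 313.3 × (2/145 + 2/123)) = 1.284.
- Actual SE: √(2 × 313.3 × [0.3717/123 + 0.0084/145 + 2 × 0.0918 × 0.1082/145]) = 1.420.
- Ratio 0.904, so type I error = 2Φ(−1.96 × 0.904) = 0.076.

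Simulated type I error (random-intercept REML, 15% random dropout, compound symmetry, 16,000 null trials per schedule, Monte Carlo SE about 0.002):

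| Model | Rows 0, 6 | 0, 6, 9 | 0, 3, 6, 9 |
|---|---|---|---|
| Group main effect kept, baseline also a covariate | 0.080 | 0.062 | 0.056 |
| Group main effect dropped, baseline also a covariate | 0.184 | 0.123 | 0.109 |
| Common baseline mean, no baseline covariate | 0.050 | 0.050 | 0.049 |

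The second model is miscalibrated even with complete data (0.163, 0.119, 0.102). For the first, complete data give 0.059 with two visits, against 0.053 without the covariate. With three or four visits the covariate leaves the SE unchanged.

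**5. Follow-up rows only, baseline as covariate.** Group-by-6-month is then the 6-month effect minus the effect at the reference follow-up visit. With a constant true effect of −4 points, its simulated mean is about zero.

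**6. Deaths.** The SAP (Handling of Missing Data) imputes 100 for assessments missed through death, which raises follow-up variance. Mortality is not given. At an assumed 3% and 6% by month 6, equal in both arms, the common-baseline model with a random intercept only gives type I error of about 0.074 and 0.086. An unstructured covariance gives about 0.061 and 0.054. A separate set of runs on rows 0, 6, 9 gave 0.062 and 0.078 for the random-intercept version, and 0.058 and 0.067 for the conventional model with baseline as covariate. There the variance ratio of 1.11 fell to about 1.03 to 1.05.

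**7. Site and setting.** Main effects remove differences in SGRQ level, not in change. If mean change differs by 4 or 8 points between inpatients and outpatients (assumed), complete-data power is 0.80 or 0.77 conventionally, against 0.85 or 0.84 with common baseline and site and setting by visit.

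**The case against.** The model class, covariates and tested term are prespecified. On the conventional reading the estimate is unbiased and planned power is met. It differs from a baseline-adjusted estimate by only about 0.34 points on average, against a 4-point target. All of this stands, and the precision loss alone would be a modest matter.

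The largest error rates (0.10 to 0.18) require dropping the group main effect while keeping baseline as a covariate. The text allows that but does not suggest it. The worst figure for the conventional model uses rows 0 and 6 only, whereas the SAP also lists the SGRQ total at 9 months and domain scores at 3, 6 and 9. The SGRQ row of the protocol's outcome table cannot be read reliably enough to settle the schedule, so the range is the honest statement.

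A common-baseline model with only a random intercept would itself be miscalibrated under the death rule. It would also sit poorly with the SAP's reason for mixed models, that changes may be subject-specific. This stands, and the fix below avoids it.

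The exploratory comparisons have a stated purpose of checking distributions, missingness and data quality. Nothing indicates that they would be used to choose the model. The case for fixing it first is ordinary prespecification.

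A reader might infer that the adjustment disappears from the test altogether. It does not: it cancels from the estimate, while the standard error can change, as step 4 shows.

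**Conclusion.** The point holds, and the change should be made. The text does not determine one primary model. On its best-supported reading, the promised adjustment does not act on the primary estimate. Entering baseline SGRQ on both sides, which a literal reading invites, makes the test mildly anti-conservative when follow-up is missing (about 0.056 to 0.08 against 0.05). The forgone gain is about four percentage points of power, less once deaths are imputed as 100.

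These sizes rest on the back-solved SD of 17.7, ρ = 0.8, compound symmetry and random dropout. The mortality rates and setting differences are assumptions. The cancellation with complete data is algebra and needs none of them.

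A reader might infer that the trial is underpowered, its primary estimate biased, or its true error rate near 18%. The documents support none of these: the conventional reading is unbiased and keeps 0.80 power, and the 18% figure belongs to a variant that no section proposes.

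**What to change.** Write one primary model into the SAP, dated before outcomes are compared by group (enrolment of 290 is already reported).

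- **Outcome rows:** SGRQ total at baseline and each follow-up visit.
- **Fixed effects:** visit; group by follow-up visit, with no group main effect so that the arms share one baseline mean; site by visit and setting by visit, with their main effects. No separate baseline covariate.
- **Covariance:** unstructured within patient, fitted by REML, or robust standard errors, instead of a random intercept only.
- **Test:** the group-by-6-month coefficient. It remains the difference in change from baseline to 6 months, now baseline-adjusted.

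Use the same form for the continuous secondary outcomes. The cost is SAP wording, with the same data and software. The downside is a few more parameters: with four visits, 4 × 5 / 2 = 10 covariance parameters instead of 2, plus the site and setting by visit terms.
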